5.5.2 Vital signs

Vital sign measurements of systolic and diastolic blood pressure, heart rate, respiratory rate, and body temperature will be summarized based on safety population. Descriptive statistics for observed values and change from baseline in the vital sign parameters will be calculated and presented by treatment arm and visit.

The by-participant listing for the vital signs results will be provided.

5.5.3 Physical examination

Physical examination includes photophobia, blurred vision, visual impairment, pruritus skin lesions compatible with scabies, and others.

The shift from baseline to post-baseline visit in the physical examination result (including "Yes", "No", "Not Determined") by the above variable will be provided for safety population.

The by-participant listing for the results of physical examinations will be provided.

5.6 Additional analyses

5.6.1 **Population pharmacokinetic analysis (phase II)**

The population PK analysis for the phase II will be reported in a separate document.

5.6.2 Participant palatability/acceptability (phase II)

The NBRs for participant overall opinion of taste, overall opinion of smell, overall opinion of texture, and parent or caregivers overall opinion on their child's acceptability of the formulation will be summarized using descriptive statistics.

5.6.3 Resistance analysis (phase III)

Analyses of anthelmintic resistance analysis will focus on *T. trichiura* and hookworms separately. In the case of hookworms (which comprise more than one species), anthelmintic resistance will be evaluated for each hookworm species if more than one species is present; we predicted that *Necator americanus* will be the predominant species. All samples determined to be positive (pre- and post-treatment) for these parasites by microscopy will be included in the resistance evaluation and grouped by treatment arm. The total number of samples included in resistance analysis has been calculated according to the efficacy estimations shown in Table 3 (see Table 5):

Species	Treatment arm	Pre- treatment samples (n)	Expected CR (%)	Post- treatment samples (n)	Total samples (n)
T. trichiura	ALB	129	23.7	99	228
	ALB+IVM	248	43.7	140	388
	ALB+IVM (x3)	248	59	102	350
	Total	625	45.4	341	966
Hookworm	ALB	101	79.5	21	122
	ALB+IVM	101	79.5	21	122
	ALB+IVM (x3)	110	95	6	116
	Total	312	84.6	48	360
TOTAL		937		389	1326

Table 5. Estimations of number of microscopically positive samples pre- and post-treatment by treatment arm and by specie.

DNA extracted from eggs collected from parasite-positive samples will undergo whole-genome sequencing, from which genetic variation within and between samples will be determined. To identify genetic variation associated to the treatment response and therefore, with anthelmintic resistance, we will measure distribution of genome-wide genetic diversity between treatment groups and throughout the genome. Genome-wide nucleotide diversity (pi), Waterson estimator, Tajima's D, Fu's and pairwise FST will be estimated in 50 kbp non-overlapping sliding windows. To improve the visualisation of the genome-wide comparisons, analyses will be restricted to scaffolds in chromosomal linkage groups. Statistical significance will be inferred by the distribution of data points, from which data points that lie great than three standard deviations from the genome-wide mean to be outliers of interest. We will identify genes in these outlier regions of genetic differentiation between parasite populations showing differences in treatment response (i.e. good responders vs poor responders, pretreatment vs post-treatment) in the three treatment arms separately and in combination.

Principal component analysis (PCA) will be used to determine if there is population genetic structure present; if there is, we use the principal component data to correct our association testing to account for this potential bias. Two different association tests will be performed: (i) a logistic regression genome-wide association between samples from participants with good treatment response phenotypes, and post-treatment samples from children with poor treatment response phenotypes; (ii) a linear regression genome-wide association analysis with the ERR estimates as a continue variable for all samples collected before treatment. For both tests, top principal components of the PCA will be used as covariates, and a Bonferroni (or other, suitable multiple-testing methods) corrected threshold will be used to determine genome-wide level of significance. We will characterise the predicted effects of genetic variation we uncover on genes, and identify relationships between genes associated with the outlier variation by functional enrichment analyses.

Finally, considering the previous association between the β -beta tubulin gene variants and resistance, we will examine this gene and genetic variants within it for associations with resistance, and within the context of all variants identified in the genome-wide analyses.

Genomic data are collected for exploratory purpose and may not be reported in the clinical study report if the sample analysis can not be finished.

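### In the exploratory genomic scan, the SAP infers statistical significance from a 3-SD cut on the genome's own windows, a rule with no null distribution or error control for treatment response

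*SAP*

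**What the plan says.** SAP 5.6.3 plans whole-genome sequencing of eggs from microscopy-positive *T. trichiura* and hookworm samples. The unit of the scan is the window: "Genome-wide nucleotide diversity (pi), Waterson estimator, Tajima's D, Fu's and pairwise FST will be estimated in 50 kbp non-overlapping sliding windows". The number of windows is not given; the SAP says only that "analyses will be restricted to scaffolds in chromosomal linkage groups".

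The decision rule is a single sentence. It opens: "Statistical significance will be inferred by the distribution of data points, from which data points that lie great than three standard deviations". Its second half, in full, takes "data points that lie great than three standard deviations from the genome-wide mean to be outliers of interest".

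The flagged windows are then put to use: "We will identify genes in these outlier regions of genetic differentiation between parasite populations showing differences in treatment response". The contrasts named are "good responders vs poor responders, pretreatment vs post-treatment) in the three treatment arms separately and in combination". Genes tied to the outlier variation also feed a functional enrichment analysis.

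Two association tests follow, one logistic and one linear. Both use top principal components as covariates, and for both "a Bonferroni (or other, suitable multiple-testing methods) corrected threshold will be used to determine genome-wide level of significance". Beta-tubulin variants are examined as well. The section closes by describing the genomic data as exploratory and possibly absent from the clinical study report.

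**The concern.** A significance statement about treatment response needs a reference distribution: how the window statistics would behave if responder or time-point labels carried no information. The SAP's reference is the spread of the statistic from one window to the next within the same scan. That spread reflects ordinary variation along the genome as well as sampling noise. If the labels were shuffled at random, the scan would still have a mean, an SD and a tail, and the rule would still mark that tail. It shows which windows are unusual in the scan, not which windows differ by response.

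The same sentence uses the language of statistical significance, and the next reads the flagged genes as differentiation linked to treatment response. A report that follows the SAP could therefore say that regions were significantly associated with response on the strength of a list that would probably have appeared without any effect.

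**Working it through.** **The plan's own figure.** None. The SAP gives no alpha, false-positive rate or window count for this scan, so there is nothing to reproduce.

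**Inputs from SAP 5.6.3.** A threshold of 3 SD from the genome-wide mean; 50 kbp non-overlapping windows; two contrasts (good v poor responders, pre v post), each in three arms separately and combined.

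**Assumption.** Number of windows M. I use 200 to 2,000, which at 0.05 Mb per window is 10 to 100 Mb.

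**Step 1: one scan, no signal, independent normal windows.** The two-sided tail is p = 2(1 − Φ(3)) = 0.00270. Expected flags = M·p, and P(at least one) = 1 − (1 − p)^M. The last column is the SD multiple that would hold one scan to a 5% two-sided family-wise error under normality.

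| M | Expected flags | P(at least one) | SD multiple for 5% |
|---|---|---|---|
| 200 | 0.54 | 42% | 3.66 |
| 500 | 1.35 | 74% | 3.89 |
| 1,000 | 2.70 | 93% | 4.06 |
| 2,000 | 5.40 | 99.6% | 4.21 |

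Solving 1 − (1 − p)^M = 0.99 gives M ≈ 1,703, about 85 Mb. If only the upper tail counts (p = 0.00135), the probabilities fall to 24% at M = 200, 49% at 500, 74% at 1,000 and 93% at 2,000.

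**Step 2: does standardising by the scan's own mean and SD change this?** No. Simulated normal windows treated that way (2,000 runs) gave 44%, 75% and 94% at M = 200, 500 and 1,000.

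**Step 3: other shapes with no signal.**
- Null FST (60 v 60 samples, no true differentiation; 20 and then 200 SNPs per window, all my choices): 84.5% and 46% at M = 200; 100% and 83.5% at M = 500; 100% and 96.5% at M = 1,000, with 7.4 and 3.2 flags on average at M = 1,000.
- Neighbouring windows correlated (autoregressive, 0.8): 60% at M = 500, 85% at M = 1,000, 95% at M = 1,500.
- Uniform windows: no flags at any M. A bounded, light-tailed statistic would escape the problem, but FST is not expected to have that shape.

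**Step 4: the planned set of scans.** For pairwise FST alone, 2 contrasts × (3 arms + combined) = 8 scans per species. Upper tail only, P = 1 − (1 − 0.00135)^(8M) = 88% at M = 200 and 99.5% at M = 500. This treats the eight as independent. They share samples, so the true figures are somewhat lower.

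**Step 5: does the later correction cover the scan?** Set side by side, no. The principal-component covariates and the Bonferroni-type threshold are specified for the logistic and linear association tests. Nothing in SAP 5.6.3 extends them to the windows.

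**The case against.** The strongest reply is that this is declared exploratory work. Outlier scans are a reasonable way to nominate genes, the SAP's own term for the flagged windows is outliers of interest, and formal genome-wide inference is left to two association tests that are adjusted and corrected. Comparing each window with the genome-wide mean also has a merit: it allows for background differentiation between groups. All of that stands, and it limits the point to what may be claimed from the scan. It does not remove the point, because the same sentence still says that statistical significance is inferred this way.

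Three stronger readings are tempting, and the documents do not support them.

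- *The scan almost surely declares significant regions.* That depends on a window count the documents do not give. For one scan with normal tails the chance is 42% at 200 windows.
- *The secondary resistance objective is compromised.* In Protocol section 3 and SAP 2.1.2.2 that objective concerns known albendazole-resistance alleles. It is served mainly by the beta-tubulin examination and by the chi-square and logistic analyses in Protocol 9.5.3. The secondary endpoint on genotypic resistance is worded more broadly, but the scan is not its only analysis.
- *The error repeats over all five statistics.* Pi, Watterson's estimator, Tajima's D and Fu's statistic describe variation within a population. Only pairwise FST directly measures differentiation between groups, which is why step 4 counts FST scans alone.

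Nor is a compulsory permutation test clearly better. Permutation assumes exchangeable samples, which fails if response tracks parasite population structure, a possibility that SAP 5.6.3 itself anticipates. It is also coarse in small cells. SAP Table 5 expects 6 post-treatment hookworm samples in the three-dose arm (110 × 0.05 = 5.5, rounded up), so within-child swapping gives at most 2^6 = 64 relabellings, before any split by hookworm species.

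**Conclusion.** The point holds as a defect in what the window scan is allowed to claim. The 3-SD rule has no null distribution and no error control for treatment response, and the correction elsewhere in the section does not reach it. In one scan with no signal, the chance of at least one flagged window runs from about 42% (200 windows) through 74% (500) and 93% (1,000) to over 99% (about 1,700 or more), and it is higher over the eight planned FST scans per species. These figures rest on an assumed window count, normal tails and independent windows. Skewed or heavy tails generally raise them; correlation between neighbouring windows lowers them. The effect is confined to the exploratory genomic analysis, and cure-rate and safety conclusions do not depend on it. The change is worth making because it costs almost nothing and alters what the trial may report about resistance.

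**What to change.** In SAP 5.6.3:

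1. Remove the statement that statistical significance is inferred from the distribution of the windows. Describe windows beyond 3 SD as candidate outliers, reported descriptively with the number of windows scanned.
2. State that any claim of significant association with treatment response rests on the two association tests, with their principal-component covariates and multiplicity-corrected threshold.
3. Optional, if a significance statement for FST windows is still wanted: calibrate it by permuting response or time-point labels within arm and site, using the genome-wide maximum or a 5% false discovery rate. Do this only where sample numbers allow and after checking population structure. Small cells such as three-dose hookworm stay descriptive.

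Items 1 and 2 cost a sentence or two and need no new samples or procedures. Item 3 adds computing time. The downside is that fewer regions can be called significant.

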# 9.5.3 ANALYSIS OF THE SECONDARY ENDPOINT(S)

Egg count reduction for each species (for *hookworms*) at end of treatment period will be estimated. *S. stercoralis* will not be evaluated by this analysis.

Version 4.0 21st January 2022

ALIVE Study

Percent egg count reduction is defined as:

(egg count at pre-treatment – egg count at post-treatment)

\_ x100%

egg count at pre-treatment

For the statistical analysis, a logarithmic transformation will be conducted. As there may be participants with a count of zero eggs in the post-treatment stool sample, a value of 1 will be added to total egg count at baseline and total egg count at post-treatment so that the logarithmic transformation can be applied. The geometric mean will be used to summarize the mean egg count at pre-treatment and post-treatment visits and in the calculation of the mean percent egg reduction. Treatment differences will be evaluated by an analysis of covariance (ANCOVA), in which the logarithm of the egg count at post-treatment is the dependent variable, site (if appropriate), and treatment as fixed effect, and the logarithm of the egg count at pre-treatment is the covariate. Baseline egg count will also be analysed as an independent variable that conditions treatment response (60).

Correlation between Kato-Katz counts and PCR will be explored through linear regression tests of Pearson's or Spearman's (according to the underlying distribution). Kappa test will be used for the evaluation of both tests in the calculation of CR.

Relevant covariates will also be included in the data analysis. Particularly, HIV infection will be assessed as a covariate in participants recruited in Mozambique.

For the resistance testing, significant associations between the presence of resistance mutations and treatment arm will be explored through stratified bivariate analysis and afterwards, adjusted through multivariate logistic regression models; statistical significance will be assessed by Chi-square test with 95% significance. Baseline counts (for hookworm and *T. trichiura*) and site of enrolment will be assessed as covariates.

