2.1.2.2 Secondary objectives

- 1. To evaluate the **efficacy** of the FDC as a single dose or 3-day single dose regimen for the treatment of hookworm and *S. stercoralis*.
- 2. To evaluate the safety of the FDC as a single dose or 3-day dose regimen for the treatment of *T. trichiura*, hookworm and *S. stercoralis*.
- 3. To evaluate the performance of PCR in calculating the primary outcome measurement (efficacy) compared to an egg counting method (Kato-Katz).
- 4. To evaluate the frequency of known ALB resistant alleles in hookworm and *T. trichiura* in the three treatment arms before and after treatment.

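### SAP 5.6.3: the good-versus-poor responder association test confounds response with sampling time, and neither association model names arm, baseline egg count or site

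*SAP*

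**What the plan says.** SAP 5.6.3 fixes the material as follows: "All samples determined to be positive (pre- and post-treatment) for these parasites by microscopy will be included in the resistance evaluation". The DNA source is eggs: "DNA extracted from eggs collected from parasite-positive samples will undergo whole-genome sequencing". Cure, in SAP 5.4, requires a post-treatment count of zero.

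Two association tests follow.

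- Test (i): "a logistic regression genome-wide association between samples from participants with good treatment response phenotypes" on one side, and "post-treatment samples from children with poor treatment response phenotypes" on the other. The section does not define good or poor response and does not give the time point of the good responders' samples.
- Test (ii): "a linear regression genome-wide association analysis with the ERR estimates as a continue variable for all samples collected before treatment".

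On adjustment: "For both tests, top principal components of the PCA will be used as covariates". No other covariate is named, and significance is judged at a genome-wide corrected threshold.

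Protocol 9.5.3 describes a different resistance analysis: presence of resistance mutations against treatment arm, first stratified and then by multivariable logistic regression, where baseline counts and "site of enrolment will be assessed as covariates". The related objective in SAP 2.1.2.2 begins "To evaluate the frequency of known ALB resistant alleles in hookworm and" and goes on to T. trichiura, by treatment arm, before and after treatment.

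**The concern.** A cured child has no eggs after treatment and so no post-treatment DNA. Test (i) takes its poor responders only from post-treatment samples. To the extent that good responders are cured children, the contrast is a before-versus-after-drug contrast. Any variant whose frequency differs between the two time points, for whatever reason, can then appear to be a variant that predicts response.

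Arm adds a second problem. Cure depends strongly on the regimen by design, so the two response groups differ in which drug they received. In test (i) arm can also be related to post-treatment genotype through drug selection, which makes it a possible confounder.

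What is at stake is how a finding is read. Genotypic albendazole resistance in the three arms is a listed phase III secondary endpoint in the protocol. A hit from test (i) could not be read as a variant that was present before treatment and predicted failure.

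**Working it through.** **1. Reproduce SAP Table 5.** Inputs: pre-treatment numbers and expected cure rates (CR) from SAP 3.5 and Tables 3 and 4. Formula: post-treatment positives = pre × (1 − CR), rounded up.

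- T. trichiura: 129 × 0.763 = 98.4 → 99; 248 × 0.563 = 139.6 → 140; 248 × 0.41 = 101.7 → 102. Total 341.
- Hookworm: 101 × 0.205 = 20.7 → 21 (twice); 110 × 0.05 = 5.5 → 6. Total 48.

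All match the table.

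**2. Split by response, taking good = cured (an assumption).** Cured = pre − post.

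| T. trichiura | ALB | FDC | FDCx3 | Total |
|---|---|---|---|---|
| Cured (pre-treatment sample only) | 30 (10.6%) | 108 (38.0%) | 146 (51.4%) | 284 |
| Not cured (post-treatment sample in test (i)) | 99 (29.0%) | 140 (41.1%) | 102 (29.9%) | 341 |

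For hookworm the counts are 80/80/104 = 264 cured and 21/21/6 = 48 not cured. Under this assumption every good-responder sample is pre-treatment and every poor-responder sample is post-treatment, so no covariate can separate response from time.

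Table 5 uses enrolment inflated for 10% loss. On the uninflated 116/223/223, not cured = 88.5 + 125.5 + 91.4 ≈ 305 and cured ≈ 562 − 305 = 257. The structure is the same.

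**3. How strongly arm drives the phenotype.** Cure proportions are 30/129 = 0.233, 108/248 = 0.435 and 146/248 = 0.589; overall 284/625 = 0.454. Between-arm share of variance = [129 × (0.233 − 0.454)² + 248 × (0.435 − 0.454)² + 248 × (0.589 − 0.454)²] / [625 × 0.454 × 0.546] ≈ 0.07. Arm explains about 7% of cure: enough to unbalance the groups, but not most of the phenotype.

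**4. Effect on a variant unrelated to response.** Simulation: 1000 runs, 625 T. trichiura children, Table 3 cure rates, 20% baseline carriage, two-sided 0.05. Carriage and shifts are assumptions; the documents give no allele frequencies.

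| Pre-to-post shift in carriage | Test (i), good = cured | Same, plus arm | Pre-treatment samples in both groups, plus arm |
|---|---|---|---|
| none | 5% | 5% | 4% |
| 5 points, all arms | 31% | 30% | 6% |
| 10 points, all arms | 82% | 79% | 6% |
| 20 points, all arms | 100% | 100% | 4% |
| 10 points, ALB only | 13% | 7% | 5% |
| 20 points, ALB only | 41% | 15% | 4% |

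Adding arm alone does not remove a shift common to all arms. Using pre-treatment samples in both groups does.

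**5. At a genome-wide threshold.** The SAP uses a corrected threshold, so 0.05 overstates the absolute risk. With alpha = 10⁻⁶ (0.05 over an assumed 50,000 tests), rejection ≈ Φ[(d − z·s₀)/s₁], where d is the shift and s₀ and s₁ are the pooled and unpooled standard errors. For 10 points: z = 4.892, pooled carriage = (284 × 0.2 + 341 × 0.3)/625 = 0.2546, s₀ = 0.0350, s₁ = 0.0343, giving (0.1 − 0.1712)/0.0343 = −2.07, or 1.9%. The same formula gives 0.03% for 5 points and 70% for 20 points. Per variant, only large shifts pass, but the bias itself remains.

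**The case against.** Several points on the other side stand.

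- **Test (ii) is sound on timing.** It compares responses using pre-treatment samples throughout. A reader might infer that no association hit under this section could be read as a pre-existing variant; that is not so for test (ii). Arm is randomised and so largely independent of baseline genotype, so leaving it out there is not a source of bias comparable to that in test (i).
- **Surviving worms are partly the signal sought.** Taking post-treatment samples from poor responders can be read as deliberate enrichment for resistant parasites. That supports keeping those samples, but in a contrast where time point is explicit. It does not support setting them against pre-treatment samples and calling the difference response.
- **Arm is not ignored elsewhere in SAP 5.6.3.** Samples are grouped by arm, and the outlier scan contrasts good with poor responders and pre with post, in each arm and combined. That sentence concerns outlier regions and does not place arm in the association models.
- **The known gene is covered to a degree.** One might infer that the SAP has no analysis of known alleles or has withdrawn the protocol's. In fact it says the beta-tubulin gene and its variants will be examined for association with resistance, and nowhere retracts Protocol 9.5.3. What is missing is the specification by arm and time point.
- **The corrected threshold** lowers false positives for small shifts, as step 5 shows. Principal components may absorb some site structure, but they are not aimed at a locus-specific before/after shift.

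Other routes to a spurious difference, such as egg pooling or sequencing batches, are not described in the documents and are not relied on here.

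**Conclusion.** The concern holds for test (i). Response is confounded with sampling time, completely if good response means cure (284 pre against 341 post for T. trichiura; 264 against 48 for hookworm). Reading the overlap as complete under any definition goes too far: the SAP never equates good with cured, and if children who remain egg-positive with a high egg reduction rate also count as good, the overlap is partial. The missing definition is itself a gap.

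Neither association model names arm, baseline egg count or site. In test (i) the arm imbalance (ALB 11% against 29%; FDCx3 51% against 30%) can bias. In test (ii) the loss is mainly of precision and of arm-specific effects, such as an albendazole-resistance variant that acts mainly under albendazole alone.

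The sizes rest on the expected cure rates. The false-positive rates also rest on assumed carriage and shifts, and show direction rather than a forecast. The SAP calls the genomic data exploratory and possibly unreported in the study report, so no efficacy or safety conclusion depends on this. It is worth correcting because the correction is nearly free.

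**What to change.** In SAP 5.6.3:

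1. Define good and poor response, and state the time point of every sample entering each test.
2. Run test (i) on pre-treatment samples of both groups.
3. Add treatment arm, baseline egg count (EPG) and site to both association models, with an arm-by-variant term.
4. Keep the post-treatment samples for a separate paired comparison, within child and by arm, among children positive at both visits. Table 5 implies up to 341 T. trichiura pairs (99/140/102) and 48 hookworm pairs (21/21/6). This retains the enrichment for surviving worms.
5. Carry over the Protocol 9.5.3 analysis of known resistance alleles by arm, with baseline count and site, so that the stated objective has a specified analysis. Whether it ranks above the genome-wide scans is for the sponsor to decide.

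The cost is SAP wording and model terms. The microscopy-positive pre-treatment samples are already in the sequencing plan, so no new samples or sequencing are needed. The small downside is that pre-treatment samples from poor responders may be less enriched for resistant worms; item 4 recovers that information. With only 6 expected FDCx3 hookworm pairs, that part will be descriptive.

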5.4.1 Secondary efficacy outcomes analysis

The analysis will be conducted on the ITT population and in the sensitivity population (per protocol)

The secondary efficacy endpoints for the phase II and phase III are the following:

- CR for *T. trichiura* 21 days after treatment, as determined by microscopy (phase II).
- CR for hookworm and *S. stercoralis* 21 days after treatment, as determined by microscopy (phase II and phase III).
- ERR for *T. trichiura* 21 days after treatment, by microscopy (phase II and phase III).
- ERR for hookworm 21 days after treatment, by microscopy (phase II and phase III).
- CR for *T. trichiura*, hookworm and *S. stercoralis*, by PCR (phase II and phase III).
- Parasite burden decrease after 21 days for *T. trichiura*, hookworm, and *S. stercoralis*, by PCR (phase and phase III).

The first 2 endpoints above regarding the CR will be analyzed using the same approach as the primary endpoint analysis.

Egg reduction rate (ERR) for each species (for *T. trichiura* and hookworms) at end of treatment period will be estimated. *S. stercoralis* will not be evaluated by this analysis.

$$ERR (geometric mean) = 1 - \frac{e^{\frac{1}{n}\sum\log(EPG \ follow \ up+1)} - 1}{e^{\frac{1}{n}\sum\log(EPG \ baseline+1)} - 1}$$

The logarithmic transformation will be conducted. As there may be participants with a count of zero eggs in the post-treatment stool sample, a value of 1 will be added to total egg count at baseline and total egg count at post-treatment so that the logarithmic transformation can be applied. The geometric mean will be used to summarize the mean egg count at pre-treatment and post-treatment visits and in the calculation of the mean percent egg reduction. Treatment differences will be evaluated by an analysis of covariance (ANCOVA), in which the logarithm of the egg count at post-treatment is the dependent variable, site (if appropriate), and treatment as fixed effect, and the logarithm of the egg count at pre-treatment is the covariate. Baseline egg count will also be analysed as an independent variable that conditions treatment response [11].

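### SAP 5.6.3 test (ii) fits ordinary linear regression to an egg reduction rate with no lower limit, so its genome-wide p-values are far too small for low-frequency variants (about 10% or less)

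*SAP*

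**What the plan says.** SAP 5.6.3 describes two association tests. Test (i) is a logistic regression on responder status. Test (ii) is "a linear regression genome-wide association analysis with the ERR estimates as a continue variable for all samples collected before treatment". On adjustment the section says: "For both tests, top principal components of the PCA will be used as covariates". On error control, a Bonferroni or other suitable "corrected threshold will be used to determine genome-wide level of significance". It names no transformation of ERR, no robust or permutation inference and no minimum allele frequency. It gives neither the number of variants nor a numeric threshold.

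ERR is defined in two places. Protocol 9.5.3 begins "Percent egg count reduction is defined as" and gives the difference between pre- and post-treatment counts divided by the pre-treatment count. SAP 5.4.1 gives a geometric-mean formula over n participants, in which "a value of 1 will be added to total egg count at baseline and total egg count at post-treatment".

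For the comparison of arms, SAP 5.4.1 does not regress ERR. It uses an analysis of covariance "in which the logarithm of the egg count at post-treatment is the dependent variable, site (if appropriate), and treatment as fixed effect", with the log baseline count as covariate.

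Protocol 9.5.3 also covers resistance testing. It plans logistic models relating mutations to arm, and would consider the pre-treatment count and the recruiting site as adjustment variables. SAP 5.6.3 does not carry these into test (ii).

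**The concern.** A Bonferroni threshold controls false positives only if each p-value is right far out in its tail. An ordinary regression p-value at 1e-5 or 5e-8 relies on residuals that are not dominated by a few observations. Per-sample ERR breaks that condition. A fall from 300 to 12 EPG scores 1 − 12/300 = 96%, but a rise from 12 to 300 EPG scores 1 − 300/12 = −2,400%. A handful of such children can carry most of the variance. A low-frequency variant that two or three of them share by chance can look genome-wide significant.

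False variants would then enter the functional enrichment work and the genome-wide context in which the SAP means to read the beta-tubulin results. Genotypic albendazole resistance is a listed phase III secondary endpoint in the protocol, although SAP 5.6.3 labels the genomic data exploratory.

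**Working it through.** **Inputs from the documents.** Pre-treatment samples (SAP Table 5): T. trichiura 129, 248 and 248 (625 in all); hookworm 101, 101 and 110 (312). Expected cure rates: 23.7%, 43.7% and 59%; and 79.5%, 79.5% and 95%. Counting is by duplicate Kato-Katz.

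**The plan's own figures.** Table 5 gives expected positive post-treatment samples as n × (1 − cure rate), rounded up:
- T. trichiura: 129 × 0.763 = 98.4 → 99; 248 × 0.563 = 139.6 → 140; 248 × 0.41 = 101.7 → 102; total 341.
- Hookworm: 101 × 0.205 = 20.7 → 21 (two arms); 110 × 0.05 = 5.5 → 6; total 48.
- Overall cure: 1 − 341/625 = 45.4% and 1 − 48/312 = 84.6%.

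All match. The SAP states no error rate for the genome scan, so there is nothing further to reproduce.

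**ERR for one sample.** With n = 1 the SAP formula is 1 − [exp(log(post+1)) − 1] / [exp(log(pre+1)) − 1] = 1 − post/pre, the same as the protocol ratio. It equals 1 for every cured child and has no floor.

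**Assumptions, not in the documents.** Lognormal infection intensities with negative binomial counts; 12 EPG per egg seen over two slides; median or geometric mean 150 to 800 EPG, with light to heavy tails; variants unrelated to ERR, coded 0/1/2 or as a pooled within-sample frequency. In the tail-weight runs both codings behaved alike. Principal components were not simulated in those runs.

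**Null rejection rate divided by nominal at 1e-5, ERR regression, T. trichiura, n = 625:**

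| Assumed egg counts | 1% | 5% | 10% | 20% | 25% | 50% |
|---|---|---|---|---|---|---|
| median 300, log-SD 1.5, k = 1 | 251 | 38 | 18 | 3.7 | – | – |
| 300/1.5, 300/1.0 and 800/1.0, k = 1 | – | 25–47 | 10–16 | 0.7–5 | – | – |
| light tail (ERR skew about −4.6) | 478 | 47 | 12 | – | 1.5 | 0.75 |
| moderate tail (skew about −7) | 746 | 86 | 26 | – | 2.5 | 0.17 |
| heavy tail (skew about −12) | 1,293 | 170 | 58 | – | 1.2 | 0 |

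The columns are allele frequencies. A further run at 30% gave 1.0. The moderate-tail row uses 600,000 tests per cell, so 600,000 × 1e-5 = 6 rejections are expected. Ratios near 1 are therefore noisy; ratios above 10 are not explained by that noise. At the 0.05 level the moderate-tail ratio is 0.92 to 1.00 at every frequency, so a check at conventional levels would not show the problem.

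**What this does to the scan.**
- If 10,000 variants shared one frequency and Bonferroni 5% were used (first row, 40 simulated trials), the chance of any false hit was 83% at 5%, 63% at 10% and 20% at 20%.
- If 1,000,000 variants were tested at 5e-8 (moderate tail), the expected false hits are 1.25e-4 × 1,000,000 = 125 if all had frequency 5%, and 1.5e-5 × 1,000,000 = 15 if all had 10%. The intended number is 5e-8 × 1,000,000 = 0.05.

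**Cause.**
- Five of the 625 children supplied 69% to 79% of the ERR sum of squares.
- Flooring ERR at 0, with the spike at 100% kept, brought the ratio to at most 1.45 down to 1e-4 and at most 1.25 at 1e-5.
- Adding arm as a covariate while keeping ERR as the outcome left 23 to 46 times nominal at 5%.

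**The log-count model on the same kind of data.**
- T. trichiura: about 0.7 to 1.7 times nominal at 1e-5 for frequencies of 5% to 10%. Family-wise error was about 3% to 10%, imprecise because it rests on 30 to 40 trials.
- Hookworm: ERR regression gave 62 to 207 times nominal at 5%. The log model still gave 2 to 4 times at 5% to 10% in some runs, and 9 to 13 times at 5% in others.

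**The case against.** **ERR per child is inferred.** SAP 5.6.3 says neither raw nor per-child, and its formula is a group mean. That is true, but a regression over samples needs one value per sample, and both definitions then give 1 − post/pre.

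**The effect is conditional.** This stands. A reader might infer that all the genome-wide p-values are invalid. They are not: the excess depends on allele frequency and threshold, and the test can be conservative at 50%. The family-wise figures above also assume that every variant has the same low frequency. But the SAP sets no frequency filter, so nothing keeps low-frequency variants out.

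**The cap at 100% is not the cause.** A reader might blame the large share of cured children. For T. trichiura the flooring result rules that out. For hookworm the tied values do matter.

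**Covariates.** A reader might infer that baseline count is missing from the trial's resistance analysis altogether, or that leaving out arm creates false hits. Neither is supported. Protocol 9.5.3 names baseline counts and site for resistance testing. Arm is randomised, so it is independent of the parasites' pre-treatment genotype, and omitting it costs only power.

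**Another multiplicity method is allowed.** The SAP leaves room for one, but any method that corrects these p-values inherits their error.

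**The analysis is exploratory.** SAP 5.6.3 says so, and adds that the results may not reach the clinical study report. The secondary objective on known resistance alleles can also be served by the beta-tubulin examination and the protocol's logistic models. This limits the consequence. It does not rescue a significance threshold that fails to control error.

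**Conclusion.** The point holds for low-frequency variants at genome-wide thresholds. For T. trichiura at allele frequencies of 5% to 10%, rejection at 1e-5 with no true association is roughly 10 to 90 times nominal under moderate assumed egg counts, and 12 to 170 times across light and heavy tails. It runs to hundreds of times or more at 1%, is small by 20% to 25%, and is absent at 30% to 50%. The direction was the same under every distribution tried. The size rests on assumed egg counts, numbers of variants and allele frequencies, none of which the documents give.

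The damage is confined to the exploratory genome scan. Nothing in the documents supports extending it to the primary cure-rate analysis, the arm comparison of egg counts on the log scale, or safety. The change is still worth making, because it is cheap and the outcome model is already in the SAP.

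**What to change.** Rewrite test (ii) in SAP 5.6.3 as follows:
- Outcome log(post-treatment EPG+1); covariates log(baseline EPG+1), site and the principal components. SAP 5.4.1 already uses this outcome ("the logarithm of the egg count at post-treatment is the dependent variable"), and protocol 9.5.3 already names baseline count and site for resistance testing. Add treatment arm for power.
- State a minimum allele frequency (5%, for example) before the scan is run.
- Take p-values for the top hits from permutation within arm and site. For hookworm this is required: about 85% are expected to be cured, and the log model alone stays inflated even at 5%.

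The cost is a short SAP edit and computing time; no new data are needed. The smallest p-value from B permutations is 1/(B+1), so reaching 5e-8 for a single hit takes about 1/5e-8 = 20,000,000 permutations. Permuting the whole scan and recording its largest statistic each time gives a family-wise threshold with far fewer. The downside is that effects are reported on the log-count scale and not in ERR points.
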